6.6.2. Nivolumab

It is recommended to continue treatment with nivolumab for clinically stable subjects with initial evidence of disease progression until disease progression is confirmed.

Dose escalation or reduction is not recommended. Dosing delay or discontinuation may be required based on individual safety and tolerability. Guidelines for permanent discontinuation or withholding of doses are described in [Table 1](#). Detailed guidelines for the management of immune-related adverse reactions are described in Nivolumab package insert.

If during the neoadjuvant phase, nivolumab is withheld or discontinued, tavo-EP can be administered as monotherapy (up to 3 4-week cycles) after discussion with principal investigator.

Table 1 Recommended treatment modifications for nivolumab

Immune-related adverse reaction	Severity	Treatment modification
Immune-related pneumonitis	Grade 2 pneumonitis	Withhold dose(s) until symptoms resolve, radiographic abnormalities improve, and management with corticosteroids is complete
	Grade 3 or 4 pneumonitis	Permanently discontinue treatment
Immune-related colitis	Grade 2 diarrhea or colitis	Withhold dose(s) until symptoms resolve and management with corticosteroids, if needed, is complete
	Grade 3 diarrhea or colitis	Withhold dose(s) until symptoms resolve and management with corticosteroids is complete
	Grade 4 diarrhea or colitis	Permanently discontinue treatment
Immune-related hepatitis	Grade 2 elevation in aspartate aminotransferase (AST), alanine aminotransferase (ALT), or total bilirubin	Withhold dose(s) until laboratory values return to baseline and management with corticosteroids, if needed, is complete
	Grade 3 or 4 elevation in AST, ALT, or total bilirubin	Permanently discontinue treatment
Immune-related nephritis and renal dysfunction	Grade 2 or 3 creatinine elevation	Withhold dose(s) until creatinine returns to baseline and management with corticosteroids is complete
	Grade 4 creatinine elevation	Permanently discontinue treatment

Immune-related adverse reaction	Severity	Treatment modification
Immune-related endocrinopathies	Symptomatic Grade 2 or 3 hypothyroidism, hyperthyroidism, hypophysitis, Grade 2 adrenal insufficiency Grade 3 diabetes	Withhold dose(s) until symptoms resolve and management with corticosteroids (if needed for symptoms of acute inflammation) is complete. Treatment should be continued in the presence of hormone replacement therapy ^a as long as no symptoms are present
	Grade 4 hypothyroidism Grade 4 hyperthyroidism Grade 4 hypophysitis Grade 3 or 4 adrenal insufficiency Grade 4 diabetes	Permanently discontinue treatment
Immune-related skin adverse reactions	Grade 3 rash	Withhold dose(s) until symptoms resolve and management with corticosteroids is complete
	Grade 4 rash	Permanently discontinue treatment
	Stevens-Johnson syndrome (SJS) or toxic epidermal necrolysis (TEN)	Permanently discontinue treatment (see section 4.4)
Other immune-related adverse reactions	Grade 3 (first occurrence)	Withhold dose(s)
	Grade 3 myocarditis	Permanently discontinue treatment
	Grade 4 or recurrent Grade 3; persistent Grade 2 or 3 despite treatment modification; inability to reduce corticosteroid dose to 10 mg prednisone or equivalent per day	Permanently discontinue treatment

Note: Toxicity grades are in accordance with National Cancer Institute Common Terminology Criteria for Adverse Events Version 5.0 (NCI-CTCAE v5.0).

Source: Nivolumab package insert 2018

7. DISCONTINUATION OF STUDY INTERVENTION AND SUBJECT DISCONTINUATION/WITHDRAWAL

7.1. Discontinuation of Study Intervention

It may be necessary for a subject to permanently discontinue study intervention prior to planned completion of treatment regimen (see Section 6.6 for stopping rules and toxicity management). If study intervention is permanently discontinued, the subject will remain in the study to be evaluated for up to 30 days post last dose of study intervention. See the SoA (Section 1.3) for data to be collected at the time of discontinuation of study intervention (30 days post last dose of study intervention).

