Definitive Surgery Phase: Surgery may be scheduled about 2-4 weeks after the last dose of nivolumab following radiologic and clinical assessment at that point. Pathologic response will be determined by institutional pathologist. Under certain circumstances, the definitive surgery may be delayed and done after completion of additional cycles of neoadjuvant therapy if decided by the treating physician investigators (surgeon and medical oncologist) to be in the best interest of the patient (or can be done earlier if study intervention(s) was discontinued due to AEs or other reasons).

Adjuvant Phase: Adjuvant therapy with nivolumab monotherapy will begin approximately 2-4 weeks following definitive surgery, but can be later as clinically indicated to allow medical clearance for systemic therapy; recovery from surgery is required (Day 1 of Cycle 4 will be determined by the treating investigator once the subject is cleared to initiate systemic therapy). Nivolumab (480 mg IV infusion on Day 1 of each 4-week cycle) will be administered for up to 9 cycles during the Adjuvant phase.

Follow up:

- All subjects will be followed for 4 weeks after last dose of nivolumab at End of Study (EOS) visit.
- In the absence of disease progression, data from standard of care imaging will be captured every 3 months for 2 years post-surgery and every 6 months thereafter for up to 3 years post-surgery.
- Long-term survival status will be performed every 6 months (by phone) for up to 5 years from study registration, unless the study is terminated early.

Protocol Monitoring Committee (PMC) review: Moffitt PMC will monitor safety and efficacy parameters as specified in the PMC section later in this protocol.

Disclosure Statement: This is a single group treatment study with 1 arm that has no masking.

Number of Subjects: Up to 33 subjects; in Simon minimax Stage 1, up to 22 subjects can be enrolled. If the number of pCR in Stage 1 meet the pre-specified number ($N \geq 3 / 22$), enrollment for Stage 2 will include an additional 11 subjects (for a total of 33 subjects).

Study Duration: For each subject, the total duration of study participation will be 1 year (excluding the Screening period), plus long-term follow-up of up to 5 years (until death, subject withdraws consent or the study was terminated):

- Screening period: up to 4 weeks
- Neoadjuvant phase: 12 weeks (Up to 3 x 4-week cycles)
- Definitive surgery phase: approximately 2-4 weeks

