1.2. Schema

Neoadjuvant

Phase

(Up to 3 x4-week cycles;
12 weeks)

- Intra-tumoral TAVO-EP on Days 1, 8 and 15 (optional) of each 4-week cycle.
- Nivolumab 480 mg IV infusion on Day 8 of each 4-week cycle.
- On Day 8, TAVO-EP will be administered prior to nivolumab infusion.

Definitive Surgery

Phase

- Surgery approximately 2-4 weeks after the last dose of nivolumab.
- Pathologic response will be determined by the institutional pathologist.
- Surgery may be done sooner or delayed if clinically indicated based on disease status and recovery from adverse events as determined by the treating physician investigator to be in the patient's best interest.

Adjuvant

Phase

(Up to 9 x4-week cycles)

- Recovery from surgery is required (Cycle 4 Day 1 is determined by the treating physician investigator once the patient is cleared to initiate adjuvant systemic therapy; Approximately 2-4 weeks following definitive surgery but can be later as clinically indicated to allow medical clearance for systemic therapy).
- Nivolumab 480 mg IV infusion on Day 1 of every 4-week adjuvant cycle, up to 9 cycles.

Follow-Up

Phase

- Subjects will follow up 4 weeks after the last dose of nivolumab (End of Study visit).
- Long term follow-up in accordance with the standard of care.
- Long term follow-up status either in clinic or via phone, but must collect information on disease status (relapse or not) and survival.

NOTE: At the discretion of the treating physician investigator and as discussed with the patient as a means of maximizing local effects of tavo, an optional additional cycle of tavo-EP can be administered during the 3rd week (Day 15) of each of the 3 neoadjuvant cycles in the absence of limiting toxicities.

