1.3. Schedule of Activities (SoA)

Period/Procedure	Screening	NeoadjuvantPhase						Definitive Surgery Phase			Adjuvant Phase	EOS / Early Discontinuation Visit [21]	Long term follow-up [22] 
		Cycle 1		Cycle 2		Cycle 3		Pre-Surgery	Surgery [18]	Post-Surgery Recovery [19]			
Study Day/ Day on cycle (1 cycle = 4 weeks)	≤-28	1	8	15	1	8	15	1	8	15	Day 1	4 weeks after last dose	~ every 6 months
Visit Window		±2 days								±7 days	±3 days	±3 days	
Informed consent	X												
Demographic and Medical History [1]	X												
Inclusion/Exclusion criteria review	X												
Concomitant medications [2]	X	X		X	X			X		X	X	X	
ECOG Performance status	X	X						X		X	X	X	
Overall Survival status													X
Physical exam and weight	X	X		X	X			X		X	X	X	
Vital signs [3]	X	X	X	X	X	XX	X	X	X	X	X	X	
Disease staging [4]	X												
Disease Evaluation by RECIST v1.1 / iRECIST [5]	X							X				X, if disease progression	
Lesion Photographs & clinical	X			X	X			X				X, if disease progression	

Period/Procedure	Screening	Neoadjuvant Phase						Definitive Surgery Phase			Adjuvant Phase	EOS / Early Discontinuation Visit [21]	Long term follow-up [22] ☎
		Cycle 1		Cycle 2		Cycle 3		Pre-Surgery [18]	Surgeon [18]	Post-Surgery Recovery [19]			
Study Day/ Day on cycle (1 cycle = 4 weeks)	≤ 28	1	8	15	1	8	15	1	8	15	Day 1	4 weeks after last dose	~ every 6 months
measurements [6]													
CBC with Differential [7]	X	X		X		X		X			X (Cycles 6, 9, 12)	X	
Blood chemistry [8]	X	X		X		X		X			X (Cycles 6, 9, 12)	X	
Thyroid Function [9]	X	X		X		X		X			X (Cycles 6, 9, 12)	X	
HIV, Hepatitis B & C, PT, PTT [10]	X												
Pregnancy test [11]	X											X	
Urinalysis [12]	X	X		X		X		X			X (Cycles 6, 9, 12)	X	
Imaging Procedures													
Imaging [13]	X							X			Per standard of care	X, if disease progression & possible	Per standard of care
Drug Administration													
Bi-dimensional tumor measurement for tavo dose calculation and tumor	X			X									

Period/Procedure	Screening	Neoadjuvant Phase						Definitive Surgery Phase			Adjuvant Phase	EOS / Early Discontinuation Visit [21]	Long term follow-up [22] 📞
		Cycle 1	Cycle 2	Cycle 3	Pre-Surgery	Surgey [18]	Post-Surgery Recovery [19]	Cycles 4-12 [20]					
Study Day/ Day on cycle (1 cycle = 4 weeks)	≤-28	1	8	15				Day 1	4 weeks after last dose	~ every 6 months			
response[14]													
tavo-EP [25]		X	X	XX	X	X	XX						
Pain Assessment [15]		X	X	XX	X	X	XX						
Nivolumab			X		X		X				X		
AE assessment [16]	X	X	X	XX	X	X	XX	X	X	X	X	X	

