All subjects will be followed for 4 weeks after last dose of nivolumab at EOS visit; data from standard of care imaging will be captured (every 3 months for 2 years post-surgery and every 6 months thereafter for up to 3 years post-surgery); long-term survival status will be determined every 6 month (by phone) for up to 5 years unless the study is terminated early.

Written IND safety reports will be submitted to the FDA by the IND sponsor, for serious, unexpected suspected adverse reactions within 15 calendar days of learning of its occurrence. If the event is fatal or is deemed to be life threatening, the report will be made within 7 calendar days. The IND sponsor will also make an assessment of whether the event constitutes an unanticipated problem posing risks to subjects or others (UP). This assessment will be provided to the IRB, which, in turn will make a final determination. If the IRB determines an event is a UP it will notify the appropriate regulatory agencies and institutional officials.

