6.4.1. Prohibited Concomitant Medications

Medications or vaccinations specifically prohibited in the exclusion criteria are not allowed during the ongoing study. If there is a clinical indication for any medication or vaccination specifically prohibited during the study, discontinuation from study therapy or vaccination may be required. The Investigator should discuss any questions regarding this with the Principal Investigator. The final decision on any supportive therapy or vaccination rests with the Investigator and/or the subject's primary physician. However, the decision to continue the subject on study therapy or vaccination schedule requires the mutual agreement of the Investigator, the Principal Investigator and the subject.

Listed below are specific restrictions for concomitant therapy or vaccination during the course of the study:

- Antineoplastic -systemic chemotherapy or biological therapy
- Immunotherapy not specified in this protocol
- Investigational agents other than nivolumab and tavo-EP
- Radiation therapy (Note: Radiation therapy to a symptomatic solitary lesion or to the brain may be allowed at the Investigator's discretion)
- Live vaccines within 30 days prior to the first dose of study treatment and while participating in the study. Examples of live vaccines include, but are not limited to, the following: measles, mumps, rubella, chicken pox, yellow fever, rabies, BCG, and typhoid (oral) vaccine. Seasonal influenza vaccines for injection are generally killed virus vaccines and are allowed; however intranasal influenza vaccines (e.g., Flu-Mist®) are live attenuated vaccines, and are not allowed.

- Systemic glucocorticoids (in dosing exceeding 10 mg daily of prednisone equivalent) for any purpose other than to modulate symptoms from an AE that is suspected to have an immunologic etiology. The use of physiologic doses of corticosteroids may be approved after consultation with the principal investigator. *Note: Topical steroids are permitted. Inhaled steroids are allowed for management of asthma.*

Subjects who, in the assessment by the Investigator, require the use of any of the aforementioned treatments for clinical management should be removed from the study.

All treatments that the Investigator considers necessary for a subject's welfare may be administered at the discretion of the Investigator in keeping with the community standards of medical care.

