7.2. Subject Discontinuation/Withdrawal from the Study

Subjects are free to discontinue their participation in the study at any time and without prejudice to further treatment. The Investigator must withdraw any subject from the study if that subject requests to be withdrawn, or if it is determined that continuing in the study would result in a significant safety risk to the subject.

Subjects who discontinue study drug or are withdrawn from the study prior to the first efficacy endpoint will not be replaced.

The subject's participation in the study may be discontinued due to the following reasons:

- Request of Investigator
- Life-threatening event or death
- Subject withdrew consent
- Subject is lost-to-follow-up

The subject may discontinue study medication due to the following reasons:

- Request of Investigator
- AE
- Treatment failure
- Subject is non-compliant with study procedures or study protocol
- Request of regulatory authority
- Pregnancy
- Other (to be specified in the electronic case report form; eCRF)

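### Section 6.4.1 removes subjects who need a restricted therapy from the study, which conflicts with the 5-year survival follow-up planned for each subject; sections 7.1 and 7.2 leave a lesser ambiguity

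*Combined protocol and SAP*

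**What the plan says.** **Planned follow-up.** The synopsis gives each subject about one year of participation, "plus long-term follow-up of up to 5 years (until death, subject withdraws consent or the study was terminated". Section 4.1 agrees: "long-term survival status will be determined every 6 month (by phone) for up to 5 years unless the study is terminated early". The schema (1.2) asks for more than vital status: "Long term follow-up status either in clinic or via phone, but must collect information on disease status (relapse or not) and survival". Stopping treatment is not among the synopsis's reasons for ending follow-up.

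**Restricted therapies.** Section 6.4.1 lists therapies restricted during the study, including systemic antineoplastic treatment, other immunotherapy and most radiation. It then says that subjects who "require the use of any of the aforementioned treatments for clinical management should be removed from the study". Earlier in the same section the stated consequence is milder: study therapy may have to be discontinued. The section closes by saying that no therapy is prohibited in the follow-up period after treatment.

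**Permanent discontinuation.** Under 7.1, "the subject will remain in the study to be evaluated for up to 30 days post last dose of study intervention". The next sentence refers to the Schedule of Activities (SoA) for the data to collect at that time.

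**Ending participation.** Section 7.2 requires withdrawal at the subject's request or "if it is determined that continuing in the study would result in a significant safety risk to the subject". It also permits participation to end for other reasons, among them a request of the investigator and "Life-threatening event or death". A separate list gives the reasons for stopping study medication.

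**Analysis.** Section 10.7.1.1 censors OS at the last date the subject was known to be alive. Relapse-free survival (RFS) counts relapse or death. Both are secondary, and 9.4 and 9.4.3 call for descriptive summaries by Kaplan-Meier methods.

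**The concern.** Kaplan-Meier estimates assume that censored subjects have the same later risk as those still followed. A subject who needs new systemic anticancer therapy probably does not. If a site takes that subject off study under 6.4.1 and stops the calls, the OS time is censored near that point and later deaths are not seen. This censoring is avoidable, because the 6-monthly calls are already planned, and it is probably informative. Reported OS would be too high if the lost subjects do worse and too low if they do better.

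RFS is less exposed. A relapse that prompts new therapy is already an event, so mainly subjects who leave before relapse are at risk.

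**Working it through.** **1. Setting the passages side by side**

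| Place | If a subject needs a restricted therapy or stops early |
|---|---|
| Synopsis, 4.1 | Survival contact continues to 5 years |
| 6.4.1, earlier text | Study therapy may be discontinued |
| 6.4.1, removal sentence | Subject leaves the study |
| 6.4.1, closing line | Post-treatment follow-up exists and permits any therapy |
| 7.1 | In the study for up to 30 days, with a pointer to the SoA |
| SoA | A combined end-of-study (EOS) and early discontinuation visit, then a long-term follow-up column |
| 4.4 | Study ends at the last survival contact of the last subject |

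The removal sentence in 6.4.1 cannot be squared with the synopsis, or with the rest of its own section, if leaving the study ends contact. Section 7.1 can be squared. The EOS visit falls 4 weeks ± 3 days after last dose, that is 25 to 31 days, which fits the 30 days.

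**2. Size of the error**

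The plan states no figure for OS or for early stopping, so there is none to reproduce. Every input except N = 33 and the 30 days is an assumption.

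Inputs: 5-year OS without stopping S5 = 0.70; proportion stopping p = 0.20 (about 7 of 33); stop time t0 = 4 months = 0.333 years; censoring time c = t0 + 30 days = 0.4155 years; hazard ratio HR after stopping 0.5 to 2; fraction f of stoppers lost at c.

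Formulas:
- λ = -ln(S5)/5
- True S(5) = (1-p)·exp(-5λ) + p·exp(-λ·t0 - HR·λ·(5-t0))
- A = (1-p)·exp(-λc); B = p·exp(-λ·t0 - HR·λ·(c-t0))
- Reported S(5) = (A+B)·[A·exp(-λ(5-c)) + (1-f)·B·exp(-HR·λ(5-c))] / [A + (1-f)·B]

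With HR = 2:
- λ = 0.3567/5 = 0.0713 per year
- 5-year OS of stoppers = 0.502, so true S(5) = 0.8 × 0.700 + 0.2 × 0.502 = 0.660
- A = 0.7766, B = 0.1930, exp(-λ(5-c)) = 0.721
- All lost (f = 1): 0.9696 × 0.721 = 0.699, error +3.9 points
- Half lost (f = 0.5): 0.678, error +1.7 points

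| HR after stopping | True 5-year OS | Error, all lost | Error, half lost |
|---|---|---|---|
| 0.5 | 72.5% | -2.5 | -1.1 |
| 1 | 70.0% | 0 | 0 |
| 1.5 | 67.9% | +2.1 | +0.9 |
| 2 | 66.0% | +3.9 | +1.7 |

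**Wider range.** With S5 60 to 80%, p 10 to 30% and HR 0.5 to 3, stopping at month 4, the error runs from -4.8 to +10.8 points if all stoppers are lost, -2.0 to +4.4 if half are, and -0.9 to +2.0 if a quarter are. Stopping at month 8 or 12 narrows the all-lost range slightly, to -4.4 to +10.3 and -4.0 to +9.8.

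**Yardstick.** The 95% half-width for a proportion with 33 subjects is 1.96·√(S(1-S)/33): 16.7, 15.6 and 13.6 points at 60, 70 and 80%.

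The model clock starts at first dose, whereas 10.7.1.1 counts OS from diagnosis. The figures therefore show scale only.

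**The case against.** The strongest reply is that continued follow-up was plainly intended, and for 7.1 it largely succeeds. A reader might infer that 7.1 ends survival contact for every early stopper after 30 days. The documents do not support that. The next sentence ties the 30 days to data collection in the SoA, and treatment completers also have an EOS visit 4 weeks after last dose before long-term follow-up begins. If reaching that visit ended survival contact, it would end it for completers too. Section 7.2 also keeps stopping medication apart from ending participation. What remains of 7.1 is an omission: it does not say that long-term follow-up goes on.

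A reader might also infer that the plan nowhere provides for follow-up of early stoppers. That is too strong. The synopsis speaks of each subject, and its end reasons do not include stopping treatment. It does not name subjects removed under 6.4.1, however, and it is one side of the conflict.

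For 6.4.1 the reply is weaker. The milder wording and the closing line of that section point to continued follow-up, but the removal sentence is an explicit instruction, placed where a site would look.

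The reply on size is fair. All rates are assumed, and in the middle case the error is small beside sampling error. It is still systematic and preventable.

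**Conclusion.** The conflict between 6.4.1 and the synopsis with 4.1 is real. Section 7.1, and the permissive reasons in 7.2 (request of the investigator, a life-threatening event the subject survives), add a lesser ambiguity.

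Severity is minor. OS and RFS are secondary and descriptive, and the Simon two-stage test of pathologic complete response is unaffected. Under the middle assumptions the error in 5-year OS is about -1 to +2 points with half of stoppers lost, and -2.5 to +4 with all lost. It vanishes if stoppers have the same hazard as the rest.

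A reader might infer that reported OS will be inflated by some 10 points. That needs 30% stopping, a hazard ratio of 3 and every stopper lost, none of which the documents show. Nor does any document show that a site has ended contact.

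**What to change.** Reconcile 6.4.1 with the synopsis and 4.1 by stating separately what ends study treatment and what ends follow-up. Stopping study intervention or needing a restricted therapy should not by itself end the scheduled relapse-status and 6-monthly survival follow-up. The exceptions are withdrawn consent and the mandatory withdrawal in 7.2.

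For clarity:
- In 7.1, say that the 30 days refers to the EOS / early discontinuation evaluation and that long-term follow-up continues after it.
- In 7.2, say whether a request of the investigator or a survived life-threatening event ends survival follow-up.
- Where consent allows, obtain survival status for any subject already taken off study for these reasons.

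No treatment-stopping or concomitant-therapy rule changes, and the OS censoring rule and 4.4 can stay as they are.

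The cost is a few sentences, with no new procedure, since the calls are already scheduled. The SoA note effective July 26, 2023 says that all patients have completed the neoadjuvant phase. The benefit is therefore limited to subjects who stop in the adjuvant phase and to the survival status of earlier stoppers still within 5 years.
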